### **Analysis of Treatment Compliance**

Treatment compliance is crucial to validate the study objectives. A compliance threshold of 90% will be implemented for proposed analyses per treatment rendered. Drug adherence will be rigorously monitored through an innovative electronic system that will provide continuously streamed real time data in addition to confirmatory manual pill count at each follow up call and scheduled visits. Assessment of compliance is an integral component at every scheduled or unscheduled evaluation and will be based on the **electronically acquired data as well as the missed doses log in the case report form (CRF)**. *A subject will be deemed noncompliant with the study intervention if he/she misses more than 21 consecutive doses at any point, or accumulate a log of 75 missed doses throughout the study.* Treatment compliance shall be compared in atorvastatin versus placebo cases as one of the secondary aims of the study.

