### Interventions and Duration

Enrolled subjects will be randomized 1-1 to atorvastatin (starting dose 80 mg PO daily) or placebo. Dosing shall continue for the 24-month follow-up period or until reaching a safety endpoint, whichever comes first. The study shall continue until all enrolled subjects, including those reaching safety endpoints, have undergone their 24 month (end of study) MRI and clinical assessment. Laboratory studies are also performed at 3 months after dose initiation. Dose de-escalation to 40 mg/day or identical placebo capsule shall be allowed at any time during the course of the study, in the case of pre-articulated side effects or laboratory abnormalities at the initial dose. At the 12 and 24-month follow up visits, clinical evaluations, and lesional QSM, brain and lesional DCEQP permeability, and peripheral blood leukocyte ROCK activity will be assessed to determine the response to atorvastatin or placebo.

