## 5. STUDY INTERVENTION

### 5.1 Intervention, Administration, and Duration

Study drug will be administered orally as a single daily dose in the morning. Subjects in the treatment group will be started on their corresponding dose 80mg of atorvastatin or placebo. Should the subject report an adverse event meeting pre-specified criteria (Adverse events Category B below), he/she will be put on the lower dose (40 mg) of drug or matched colored placebo capsule.

Administration of study drug shall continue once daily dose in the morning for 24 total months with scheduled visits and repeat imaging at 12 and 24 months from enrollment, unless the subject reaches attrition or a safety endpoint before then. If new symptoms arise at any point after starting the study intervention subjects will be contacted by the study-designated TN for further assessment and be provided with instructions regarding continuation of study intervention based on the study adverse events management protocol (Section 7).

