### **9.3.2 Potential Missing Data, Attrition and Premature Trial Endpoint**

We considered all potential causes of missing data and we developed strategies to minimize and mitigate them. In initial pilot studies, 34 of 177 (19%) QSM assessments in CA patients were unusable due to technical reasons (mostly patient movement during image acquisition). We eliminated this problem in the most recent 25 consecutive cases with specific patient instructions. We now implement a further step of reviewing the QSM acquisition, and rapidly processing it (10 minutes on local Matlab computer terminals in our laboratory). This allows us to repeat the QSM acquisition if needed, before proceeding with contrast injection for DCEQP measurements. This “chaperoned biomarker acquisition” reduces to virtually zero the rate of missing QSM measures (See letter by [name] and Protocol Section 6.5). We nevertheless project up to 10% missing biomarker data related to imaging (claustrophobia, etc.). We further project an additional 10% missing data due to imperfect follow-up, higher than that recorded in recent trials conducted by our teams (113, 114).

Up to 20% of subjects randomized to atorvastatin (10% of trial subjects) might not tolerate the 80 mg/day dose. Many will continue the drug at the lower dose. In fact, **serious side effects or intolerance of the lower dose are expected to result in attrition in less than 5% of cases**, per extensive meta-analyses of trial experience with the study drug (See Protection of Human Subjects; and Protocol section 7.3). Another **20-30% of cases might reach a prespecified study endpoint** because of SH, and they would also stop the drug before the end of the 2-years follow-up. All subjects who stop the drug, and those with non-compliance as defined, will still be followed for the full 2 years with scheduled clinical and imaging assessments, and will be included in the **primary analysis per intention-to-treat**.

To permit secondary analysis per treatment rendered, at the power and Type I error described above, we decided to **expand the sample size by an ample 37.5%, factoring the highest combined estimates of missing data and attrition.**

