### **9.5 Data analysis**

Exploratory analyses for quality assurance and understanding of missing data patterns and distributions will be performed on the outcomes and all measurements to be used in the primary and secondary analyses. For the **primary aim**, a linear mixed model will be used that adjusts for gender to evaluate the difference between the two arms in the QSM change of the index hemorrhagic lesion per patient. Adjustment for gender is necessary because the patients will be randomized by gender stratification. Not control-

ling for stratification variables can lead to upwardly biased standard errors and a decreased power (116). The model accounts for within-patient correlation between the measurements (117, 118). Patients with outcome measurements in both periods will be included in the initial intention-to-treat analysis. A secondary analysis of the percent QSM change per year shall be conducted per treatment rendered for all patients with at least one annual epoch of measurements. Significance levels are assumed as per sample size calculations.

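### The fixed count of 75 missed doses matches the 90% compliance threshold only for a full 24-month course, and the plan does not say which rule governs when dosing ends early

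*Combined protocol and SAP*

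**What the plan says.** Section 9.5, under Analysis of Treatment Compliance, gives a percentage: "A compliance threshold of 90% will be implemented for proposed analyses per treatment rendered". The same paragraph then says when a subject is noncompliant: if the subject "misses more than 21 consecutive doses at any point", "or accumulate a log of 75 missed doses throughout the study". It does not say whether the count is meant to implement the percentage or is a separate rule. It names no denominator, and it does not say whether doses after the drug is stopped are logged as missed.

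Planned exposure is in Section 5.1: "Administration of study drug shall continue once daily dose in the morning for 24 total months". The Synopsis allows it to be shorter: "Dosing shall continue for the 24-month follow-up period or until reaching a safety endpoint, whichever comes first". Section 9.3.2 expects this to be common: "20-30% of cases might reach a prespecified study endpoint" because of symptomatic hemorrhage, and these subjects stop the drug.

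Section 9.5 (Data analysis) describes the secondary analysis as "conducted per treatment rendered for all patients with at least one annual epoch of measurements". Sections 8 and 9.3.2 keep subjects who stop the drug in follow-up, with imaging to 24 months.

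**The concern.** An absolute count corresponds to a percentage at only one length of exposure. Here that length is the full 24 months, yet the protocol itself ends dosing early for subjects who reach a safety endpoint. For them the two rules in one paragraph can give different answers about the same person.

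The classification decides who enters the treatment-rendered analyses, which Section 9.5 applies to QSM change and to the other outcomes. It also feeds the atorvastatin-versus-placebo compliance comparison, which is a secondary aim. Section 9.3.2 says the 37.5% enlargement of the sample was made to allow the treatment-rendered analysis at the stated power and Type I error. If the governing rule is left open, it may be chosen after the data are in hand.

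**Working it through.** **Inputs.** One dose a day for 24 months (Section 5.1), taken as 730 doses, or 365 for 12 months. Threshold 90%; noncompliance at 75 missed doses, or at more than 21 in a row (Section 9.5). The largest total that is not noncompliant by the count is therefore 74.

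**Formulas.** Misses allowed at 90% = 0.10 × scheduled doses, rounded down. Adherence = 1 − missed/scheduled.

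**Step 1: the plan's own figure.** 0.10 × 730 = 73, against the stated 75. In percentage terms 75/730 = 10.3% missed, or 89.7% adherence. The count and the threshold agree to within two doses over a full course, so 75 reads as a rounded 10%.

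**Step 2: shorter dosing.** Scheduled doses are those up to the day dosing ends, and later doses are assumed not to be logged as missed.

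| Months dosed | Scheduled doses | Misses allowed at 90% | Adherence at 74 misses | Totals on which the rules disagree |
|---|---|---|---|---|
| 12 | 365 | 36 | 79.7% | 37-74 |
| 18 | about 548 | 54 | 86.5% | 55-74 |
| 21 | about 639 | 63 | 88.4% | 64-74 |
| 24 | 730 | 73 | 89.9% | 74 |

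At 12 months, 74/365 = 20.3% missed. With the ±4-week visit window (Section 6.2.5), scheduled doses run from about 337 to 393, and 74 misses is 22.0% to 18.8%.

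**Step 3: does the 21-dose rule close the gap?** No. Three separate runs of 21 and one of 11 total 3 × 21 + 11 = 74 misses, and no run exceeds 21.

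**Step 4: sensitivity to what is unstated.** Take a subject whose dosing ends at 12 months.
- If later doses are logged as missed, about 365 are added. The subject is then noncompliant by the count and by the 21-dose rule, even with perfect adherence up to the stopping day.
- If they are not logged and 90% is judged on the doses scheduled while on treatment, 37 or more misses fails.
- If they are not logged and 90% is judged on the planned 730, 73 misses passes (73/730 = 10.0%), although on-treatment adherence is 1 − 73/365 = 80.0%.

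**Step 5: withheld doses.** Section 7.2 provides for withholding the study drug for 2-4 weeks after certain adverse events, which is 14 to 28 doses. A hold of 22 to 28 doses would trip the 21-dose rule if withheld doses count as missed. The plan does not say whether they do.

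**How many subjects.** 20-30% of 80 is 16 to 24 who might stop early for hemorrhage. The plan gives no basis for estimating how many of them would fall in the range where the rules disagree.

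**The case against.** The best defense is that the count is simply 90% in practical form. Over 24 months it is, and with a ±4-week window around the final visit (about 702 to 758 doses, so 10% is 70 to 76) the figure of 75 lies inside the range. A reader might infer that the two rules contradict each other in general. The documents do not support that.

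A reader might also infer that a subject at about 80% adherence will be counted as compliant in the treatment-rendered analysis. That does not follow either. The rule named for that analysis is the 90% threshold, and 79.7% fails it if it is computed on actual exposure. The subject gets in only if the count alone implements the threshold, or if the denominator is the planned course. Section 9.3.2 refers to noncompliance as already defined, and the count and run rules are the only definition given, so the first reading is natural but not stated.

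It would be wrong to assume that a subject with one measured epoch had one year of dosing. A one-epoch subject may have unusable imaging and a full 730 doses scheduled, and an early stopper is still imaged and may supply two epochs. Nothing in the plan shows that low-adherence epochs come mostly from subjects with shorter follow-up.

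Nor is it a defect of the count that all the permitted misses of a full-course subject could fall in one year. A plain 90% rule over the whole study would equally allow 73 in one year (80.0% for that year). Judging compliance per epoch is a preference, not something the plan requires.

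Finally, electronic reminders and three-monthly calls (Section 5.4) make a total near 74 in one year a worst case. What stands is narrower: the count does not scale, and neither the denominator nor the governing rule is stated for subjects who stop early.

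**Conclusion.** The point holds in limited form. The fixed count matches the 90% threshold for a full course to within two doses. For a subject whose dosing ends early, the two rules can classify the same person differently. At 12 months they disagree for totals from 37 to 74, down to 79.7% adherence, and the range narrows to a single dose at 24 months.

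The 79.7% figure rests on two assumptions: that the denominator is the doses scheduled up to stopping, and that doses after stopping are not logged as missed. Section 9.3.2 points toward the second by naming drug stoppers separately from noncompliant subjects, but no section states it. If those doses are logged, the opposite problem arises, and a fully adherent early stopper becomes noncompliant.

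The effect is confined to the treatment-rendered analyses and the compliance comparison; its size on the treatment estimate cannot be derived from the plan. The primary analysis is unaffected. The change is still worth making, because a stated rule misclassifies shorter exposures in a trial that expects them.

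**What to change.** In Section 9.5, for the treatment-rendered analyses and the compliance comparison:

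1. State that the 90% rule governs.
2. Replace the fixed 75 with more than 10% of the doses scheduled during the subject's on-treatment period. That allows 73 misses of 730 and 36 of 365.
3. State how doses after protocol-directed discontinuation, and doses withheld under Section 7.2, are counted, both in the 10% calculation and under the 21-dose rule.

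Settle this before any treatment-rendered analysis is run. Compliance per annual epoch may be added as a sensitivity analysis but is not required.

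The cost is a change of wording. The electronic adherence record and the log of missed doses are already planned. A few subjects may leave this secondary analysis.

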## 10. DATA COLLECTION, SITE MONITORING, AND ADVERSE EXPERIENCE REPORTING

### 10.1 Records to Be Kept

Participation in this study requires that original study documents be retained for a minimum of 2 years following the end of the trial. This standard complies with U.S. FDA regulations (21 CFR §312.62[c]). Records must not be destroyed without first contacting *the study investigator to ensure that the time limits defined in the regulations have been met.*

For the purposes of this section, “original study documents” are defined as:

Subject records created at or available to the study center during the subject’s participation in the trial, or any other document that supports entries in the EDC system and represents the original source of that information, including but not limited to applicable sections of medical charts, patient correspondence, laboratory data, pharmacy logs and drug accountability forms, as well as any forms or documents used to compile or maintain original subject data or study procedural information.

All Essential Regulatory Documents [as defined under Good Clinical Practice (GCP) Regulations] including: all material communications with the IRB; all communications that are related to study subjects or which otherwise document material study-related procedures or safety issues. All study documents should be uploaded to the source documents section of the database. The database will be used as the master repository for all site and Sponsor regulatory documents

### 10.2 Role of Data Management

The trial investigator will permit trial related monitoring, audits, IRB review, and regulatory inspections by providing direct access to source data and documents. Data for each subject will be reported and recorded on electronic case report forms. Electronic case report forms (eCRF) must be completed for every randomized subject.

### 10.3 Quality Assurance

AT CASH EPOC will have a robust safety and data monitoring program in full compliance with NIH policy of 10-Jun-1998 as expanded by NINDS guidelines published 14-Sep- 2011 in addition to compliance with all applicable U.S. and international GCP regulations. This program, designed to safeguard the well-being of study participants and to ensure scientific integrity, will include the following components:

- Oversight by the DCC, Clinical Coordinating Center (CCC), and IRB
- A dedicated independent medical safety monitor (IMSM) and safety compliance officer;

- Automated data quality checks at the time of eCRF completion by the investigational site;
- Dedicated independent data monitoring and quality assurance (QA) teams (Emissary International);

The components of this multifaceted approach, including each dedicated team's specific responsibilities, are discussed below.

#### **10.3.1. Data Coordinating Center (DCC)**

The DCC will provide an independent review of the research, interim safety and efficacy data, and progress towards achieving the goals of the study. To enable the CCC to properly manage the trial, the project leadership, and key personnel will jointly work on a data monitoring plan early in the process. After the award but before the project begins, the CCC will work with the DCC to develop a detailed monitoring plan. The monitoring plan will describe the process for reporting adverse events to the IRB, IMSM, and NIH.

Interim safety analyses will be prepared for the DCC on a pre-arranged schedule to evaluate efficacy and safety. Safety events will trigger a "suspend recruitment and review" by the DCC. Prior to IMSM report generation, the case report forms will be finalized, data compiled, all requested analyses conducted, and suitable reports, tables and graphs prepared. All deaths will be reviewed.

#### **10.3.2. Data and safety monitoring**

The study is designed as a single-site trial investigating one minimal-risk intervention. Per approval by NINDS, subjects' safety will be monitored by the PI and safety monitoring team as described above. The PI will be actively involved in reviewing the progress of each subject and will notify the IRB as well as the external IMSM and the NINDS program official about adverse events and unexpected problems that may influence their decision to allow the trial to continue.

**Independent Medical Safety Monitor (IMSM):** The study PI will nominate an independent experienced physician with relevant expertise who is not in affiliation with the study site at University of Chicago Medicine or the data coordinating center at Johns Hopkins University and has no conflict of interest. The IMSM will oversee ongoing monitoring of reports of SAEs in real time to ensure GCP and to identify safety concerns quickly. The IMSM will also serve as a resource to the principal investigator to provide advice about management of AEs/SAEs but will not be involved in other aspects of the trial. The IMSM may suggest protocol modifications to prevent the occurrence of particular AEs. To maximize safety considerations, the IMSM will evaluate SAEs per treatment assignments labeled A or B. In the event of unexpected SAEs or an unduly high rate of SAEs, the IMSM may request identification of A or B as treatment versus placebo. And he/she will promptly contact the PI and the NINDS program officials. The IMSM will be assisted by two designated external safety consultants, with expertise in CCM disease and in statin therapy respectively.

**Safety Compliance Officer (SCO):** The study PI and IRB require a process for timely communication of adverse events and complication rates to regulatory agencies. Thus, an essential component of this process is the safety compliance officer (SCO). The SCO will have the day-to-day responsibility of ensuring that adverse events are promptly collected, medically reviewed by the PI or IMSM and appropriately reported to regulatory agencies in compliance with GCP standards. The SCO and the statistician at the Baltimore site shall be responsible for preparing and communicating incoming documents and reports to the PI and IMSM. Inclusion/exclusion criteria, review-of-system reports, medical history, medical events, and radiographic imaging entries will be cross-checked and reviewed by applying real- time database algorithms, crosschecking sentinel dates and times, procedures, AEs, SAEs, and protocol timelines. As aggregate data reports and quarterly and annual progress reports are prepared, the SCO will query the TN and study coordinator as needed and follow the data entry tasks to completion. The SCO will serve as the liaison between the IMSM and the PI and CCC personnel to garner additional information as needed and to elicit agreement or disagreement of the CCC with the IMSM's assessment. The SCO will manage the development and revision of trial protocols, Manual of Operations and Procedures (MOP), standard operating procedure (SOP), and protocol working guidelines with the trial leadership.

**Reporting Dictionary and Data Standards:** The SCO will work closely with the trial vendors to develop the EDC systems and the corresponding paper CRFs, used for all safety-related events. The Common Terminology Criteria for Adverse Events (CTCAE) dictionary has been adapted to allow for trial-specific reporting using standardized Medical Dictionary for Regulatory Activities (MedDRA) coding.

#### **10.3.3 Automated Data Quality Checks in the EDC System**

VISION® EDC System: The EDC system has a robust set of data quality checks that will be executed at the time of data entry at the investigational site. This includes the standard validations available with most EDC systems such as range checks (e.g., to flag a high liver function test as incompatible with inclusion criteria, or to ensure a temperature is not an impossible value) and data format checks (to flag an invalid date). Additionally, our VISION platform will perform very sophisticated cross-form computed calculations that would not be available in lesser EDC systems. For example, VISION will conduct a series of verifications looking at lab values, demographics, etc. and give the site guidance regarding the eligibility of the patient for randomization using complex cross-page computations. It will also detect when the CCC has made a protocol variance and present a list of such issues to the investigator and the monitoring team for evaluation and follow-up. Consequently, our EDC system will handle much of the consistency, completeness, and logic checks immediately at the time of data collection that normally would have to be done by the monitoring team and/or offline using statistical analysis that do not typically occur until weeks or months after the patient visit. This capability therefore will result in cleaner data that will be more likely to distinguish a treatment effect and significantly reduce the cost of, and delays for, monitoring and data cleaning activities.

#### **10.3.4 Independent Data Monitoring and Quality Assurance Team**

It is important to use an independent Contract Research Organization (CRO) for monitoring and quality assurance, to provide the highest level of integrity, industry- proven best practices, and professionally trained monitors. Our **CRO, Emissary International**, maintains a team of high-caliber, fully qualified monitors in the U.S. This team will be responsible for near real-time review of the clinical data entered into our EDC system against source medical records (i.e., Source Document Verification or SDV) as well as generation and resolution of the associated data queries.

**QA Monitoring Plan:** In accordance with recently drafted FDA recommendation for risk-based monitoring approaches, this trial will employ centralized monitoring and an EDC system to:

- Replace on-site monitoring for activities that can be done better using centralized reviewers;
- Verify source medical records remotely to ensure data integrity, reduce transcription errors, and identify any undocumented safety events;
- Utilize EDC real-time data quality checks to assess range, consistency, and completeness of data at the time of entry; and
- Employ frequent statistical analyses of study data to evaluate individual subject data for plausibility and protocol compliance.

